13.4. Statistical and Analytical Methods

13.4.1 Hypothesis Testing

The study primary hypothesis is the (statistical) one-sided superiority of a TVB-2640 50-mg dose over placebo based on the primary efficacy endpoint at the 0.05 significance level, where a higher responder proportion is a better outcome. The statistical analysis (one-sided) test (CMH) of the primary hypothesis is declared if $p < 0.05$.

Mathematically, the null and alternative hypotheses for the primary efficacy endpoint are stated as:

$$H_0: p_T \leq p_p$$

$$H_a: p_T > p_p$$

Here, p_T is the proportion of responders in the TVB-2640 50-mg treatment group and p_p is the proportion of responders in the placebo treatment group.

Both one-sided and two-sided 0.05 significance level tests will be used for the secondary efficacy endpoints. For each endpoint, the SAP will specify whether the test of significance is one- or two-sided along with the expected direction of effect.

13.4.2 Analysis Sets

13.4.2.1 Intention-to-Treat Population

The principal analysis of the primary and secondary efficacy endpoints will be based on the Intention-to-Treat (ITT) population, which comprises all randomized subjects; this population will serve as the basis for all efficacy analyses. Subjects' data will be analyzed according to their randomized treatment assignment.

13.4.2.2 Modified Intention-to-Treat Populations

Modified Intention-to-Treat (mITT): Comprises all subjects in the ITT population who have completed at least 42 weeks of treatment and have an evaluable posttreatment histological assessment. Interim Analyses Modified Intention-to-Treat Population

Modified Intention-to-treat (IAmITT): Comprises a subset of subjects in the ITT population with $8\% \geq$ MRI-PDFF at screening or at baseline with at least 1 evaluable post-Baseline MRI-PDFF value, defined as an MRI-PDFF assessment obtained at least 22 weeks after the first dose of study drug.

13.4.2.3 Safety Population

The Safety population will consist of all randomized subjects who received at least 1 dose (partial or complete) of study drug. This population will be used for all summaries of subject accountability, demographic and baseline data, and safety information, including AE incidence, clinical laboratory data, ECG data, and vital signs data. Subjects' data will be summarized according to the treatment they received.

13.4.2.4 Pharmacokinetic Population

The PK population will comprise all ITT subjects with available PK measurements.

13.5. Power Considerations and Sample Size Determination

The study is powered to test the one-sided (statistical) superiority hypothesis stipulating that a TVB-2640 50-mg dose provides better benefit than placebo based on the primary efficacy endpoint. The study estimated total sample size is approximately 162 randomized subjects (108 on TVB-2640 and 54 on placebo). The sample size was derived using the normal approximation to the binomial distribution, and the estimated power to detect a difference in the primary efficacy response of 20% (TVB-2640 40% and placebo 20% at Week 52) was at least 80% (one-sided test at the 0.05 significance level). A 2-to-1 randomization allocation was assumed (TVB-2640 to placebo), and an anticipated dropout rate of 18.5% was also applied to estimate the final total sample size (N=162).

13.6. Interim Analysis

A single (secondary endpoint) efficacy interim analysis is planned when approximately 60 subjects with an MRI-PDFF value of $\geq 8\%$ liver fat at Baseline have completed Week 26 or an Early Termination visit after Week 22. The purpose of the proposed interim analysis is to examine the TVB-2640 benefit over placebo based on a Week 26 secondary efficacy endpoint consisting of “proportion of MRI-PDFF $\geq 30\%$ responders, where an MRI-PDFF $\geq 30\%$ responder is defined as a subject with $\geq 8\%$ liver fat content at Baseline who achieves a percent change (reduction) from Baseline in MRI-PDFF $\geq 30\%$.”

Interim safety summaries will accompany the interim analyses of the secondary efficacy endpoint.

An interim analysis of the primary efficacy endpoint is not feasible since the primary endpoint is only evaluated at Week 52, and not Week 26. Therefore, a statistical penalty is not envisaged in conjunction with the Week 26 interim analysis of the above-stated secondary endpoint. Interim summaries of safety and selected biomarker data will accompany the interim efficacy analysis of the secondary efficacy endpoint.

13.7. Planned Study Committees

An independent data monitoring committee (IDMC) will be established by charter to provide independent review and assessment of study data and to monitor the overall study conduct in a systematic manner to safeguard the safety of study subjects. Periodic meetings will occur as outlined in the IDMC charter. An interim analysis, which will be reviewed by the IDMC, will be performed when approximately 60 subjects with an MRI-PDFF value of $\geq 8\%$ liver fat at

Baseline have completed the Week 26 visit or an Early Termination Visit after Week 22. The IDMC will be provided with selected biomarker and safety interim results to allow for a more complete examination of the totality of the data. Upon review of the interim analysis findings, the IDMC may communicate with the Sponsor by making recommendations to the Sponsor to continue, amend, or stop the study based on these interim analysis results. The Sponsor will maintain its blind to any individual treatment assignments.

14. ETHICS

14.1. Good Clinical Practice Compliance

The Sponsor and any third party to whom aspects of the study management or monitoring have been delegated will undertake their assigned roles for this study in compliance with all applicable industry regulations and International Council for Harmonisation (ICH) Good Clinical Practice (GCP) Guideline E6.

The Investigator also must undertake to perform the study in accordance with ICH GCP Guideline E6 and applicable regulatory requirements and guidelines.

ICH GCP Guideline E6 is available at:

https://database.ich.org/sites/default/files/E6_R2_Addendum.pdf

14.2. Institutional Review Board or Independent Ethics Committee

The IRB/IEC will review all appropriate study documentation in order to safeguard the rights, safety, and well-being of the subjects. The study will only be conducted at study centers where IRB/IEC approval has been obtained. The protocol, Investigator's Brochure, informed consent form, advertisements (if applicable), written information given to the subjects (including diary cards), safety updates, annual progress reports, and any revisions to these documents will be provided to the IRB/IEC by the Investigator.

The final study protocol, including the final version of the informed consent form, must be approved or given a favorable opinion in writing by an IRB/IEC as appropriate. Written IRB/IEC approval must be received by Sagimet Biosciences or designee before a site can enroll any subject into the study.

The Investigator is responsible for informing the IRB/IEC of any amendment to the protocol in accordance with local requirements. In addition, the IRB/IEC must approve all advertising used to recruit subjects for the study. The protocol (and other amended study documents) must be re-approved by the IRB/IEC upon receipt of amendments and annually, as local regulations require. The Investigator is also responsible for providing the IRB/IEC with reports of any reportable serious adverse drug reactions from any other study conducted with the investigational product. Sagimet Biosciences will provide this information to the Investigator.

Progress reports and notifications of serious adverse drug reactions will be provided to the IRB/IEC according to local regulations and guidelines.

To ensure compliance with GCP and all applicable regulatory requirements, Sagimet Biosciences or designee may conduct a quality assurance audit. Please see Section 15.6 for more details regarding the audit process.

14.3. Ethical Conduct of the Study

The study will be performed in accordance with ethical principles that have their origin in the Declaration of Helsinki and are consistent with ICH GCP, and applicable regulatory requirements.

14.4. Written Informed Consent

The Investigator(s) at each center will ensure that the subject is given full and adequate oral and written information about the nature, purpose, possible risk and benefit of taking part in the study. Subjects must also be notified that they are free to discontinue from the study at any time. The subject should be given the opportunity to ask questions and allowed time to consider the information provided. This process should be recorded in the subject's source documentation.

The subject's signed and dated informed consent must be obtained before conducting any study procedures. Documentation of the consenting process must be recorded in the subject's source documents.

A separate signature documenting informed consent will be required for subjects who provide a blood sample for research regarding genomics pertaining to NASH with fibrosis (Section 11.2.1).

If medical photographs are requested to document an AE (Section 12.1.2), a separate signature documenting informed consent will be required before any photographs are taken.

The Investigator(s) must maintain the original, signed informed consent form(s). A copy of the signed informed consent form must be given to the subject, and this must be documented in the subject's source documents.

14.5. Subject Confidentiality

In order to maintain subject privacy, all eCRFs, study drug accountability records, study reports, and communications will identify the subject by the assigned subject number. The Investigator will grant monitor(s) and auditor(s) from the Sponsor or its designee and regulatory authority(ies) access to the subject's original medical records for verification of data gathered on the eCRFs and to audit the data collection process. The subject's confidentiality will be maintained and will not be made publicly available to the extent permitted by the applicable laws and regulations.

15. ADMINISTRATIVE REQUIREMENTS

15.1. Study Monitoring

Monitoring and auditing procedures developed by the Sponsor or designee will be followed, in order to comply with GCP guidelines.

Before a study center can enter a subject into the study, a representative of Sagimet Biosciences or designee will visit the study center to:

- Determine the adequacy of the facilities.
- Discuss with the Investigator(s) and other personnel their responsibilities with regard to protocol adherence, and the responsibilities of Sagimet Biosciences or its representatives. This will be documented in a Clinical Study Agreement between Sagimet Biosciences and the Investigator.

During the study, a monitor from Sagimet Biosciences or designee will have regular contacts with the study center, for the following:

- Provide information and support to the Investigator(s).
- Confirm that facilities remain acceptable.
- Confirm that the investigational team is adhering to the protocol that data are being accurately recorded in the source documents and eCRFs, and that investigational product accountability checks are being performed.
- Perform source data verification. This includes a comparison of the data in the eCRFs with the subject's medical records at the hospital or practice, and other records relevant to the study. This will require direct access to all original records for each subject (e.g., clinic charts).
- Record and report any protocol deviations not previously sent to Sagimet Biosciences.
- Confirm AEs and SAEs have been properly documented in the eCRFs and confirm any SAEs have been forwarded to the Sponsor or designee, and those SAEs that met criteria for reporting have been forwarded to the IRB/IEC.

The monitor will be available between visits if the Investigator(s) or other staff needs information or advice.

15.2. Case Report Form Completion

The Sponsor or designee will provide the study centers with eCRFs for each subject.

eCRFs will be completed for each study subject. It is the Investigator's responsibility to ensure the accuracy, completeness, and timeliness of the data reported in the subject's eCRF. Source documentation supporting the eCRF data should indicate the subject's participation in the study and should document the dates and details of study procedures, AEs, and subject status.

The Investigator, or designated representative, should complete the eCRF as soon as possible after information is collected, preferably on the same day that a subject is seen for an

examination, treatment, or any other study procedure. Any outstanding entries must be completed immediately after the final examination. An explanation should be given for all missing data.

The Investigator must electronically sign and date the Investigator's Statement at the end of the eCRF to endorse the recorded data.

15.3. Computerized Systems/Medical Records as Source Data

All study data recorded on source documents are to be transcribed into the eCRFs.

Clinical data will be entered by site personnel on eCRFs for transmission to the Sponsor. Data on eCRFs transmitted via the web-based data system must correspond to and be supported by source documentation maintained at the study site.

All study forms and records transmitted to the Sponsor must only include coded identifiers such that directly identifying personal information is not transmitted. The primary method of data transmittal is via the secure, internet-based EDC system maintained by Syneos Health. Access to the EDC system is available only to authorized users via the study's internet website, where a user unique assigned username and password are required for access.

Any changes made to data after collection will be made through use of the EDC system.

eCRFs will be considered complete when all missing and/or incorrect data have been resolved.

15.4. Source Documents

Source documents are considered to be 'all information in original records and certified copies of original records of clinical findings, observations, data, or other activities in a clinical study necessary for the reconstruction and evaluation of the study'. The Investigator will provide direct access to source documents and/or source data in the facilitation of trial-related monitoring, audits, review by IRB/IEC, and regulatory inspections.

The Investigator/institution should maintain adequate and accurate source documents and trial records that include all pertinent observations on each of the site's trial subjects. Source data should be attributable, legible, contemporaneous, original, accurate, and complete. Changes to source data should be traceable, not obscure the original entry, and be explained where necessary.

15.5. Retention of Records

The Investigator will maintain all study records according to ICH GCP and applicable regulatory requirement(s). Study records and source documents must be preserved for at least 15 years after the completion or discontinuation of/withdrawal from the study, and at least 2 years after the last marketing application approval or 2 years after formal discontinuation of the clinical development of the investigational product or according to applicable regulatory requirement(s).

If the Investigator withdraws from the responsibility of keeping the study records, custody must be transferred to a person willing to accept that responsibility. The Sponsor must be notified immediately by telephone or e-mail and the notification confirmed in writing if a custodial change occurs.

15.6. Audits and Inspections

Authorized representatives of Sagimet Biosciences or designee, a regulatory authority, or IRB/IEC may visit the study center to perform audits or inspections, including source data verification. The purpose of an audit or inspection is to systematically and independently examine all study-related activities and documents to determine whether these activities were conducted, and data were recorded, analyzed, and accurately reported according to the protocol, ICH GCP, and any applicable regulatory requirements.

The Investigator should contact Sagimet Biosciences or designee immediately if contacted by a regulatory agency about an inspection.

15.7.

APPENDIX A. ALGORITHM FOR EVALUATING SUBJECTS FOR POTENTIAL DRUG-INDUCED LIVER INJURY

During the study, aminotransferase elevations are to be managed as follows:

1. Isolated aminotransferase elevation (i.e., total bilirubin - normal):

ALT or AST	Event during the study	Action
Baseline ALT and AST within normal range	Increase $\geq 5 \times$ ULN	Repeat liver profile (AST, ALT, bilirubin) and PT/INR within 2 to 3 business days from the date results are received for review. Monitor the subject as per “close observation” definition* in the DILI guidance.
ALT or AST above normal range at Baseline	Increase $\geq 3 \times$ Baseline result, but no liver related symptoms (e.g., anorexia, nausea, vomiting, right upper quadrant pain, pruritus, cholestasis)	Interrupt study drug for at least 15 days. Initiate potential DILI evaluation for alternative etiologies, and repeat liver profile and PT/INR within 2 to 3 business days from the date results are received for review, and place subject under “close observation” as defined in the DILI guidance.
ALT or AST above normal range at Baseline	Increase $\geq 3 \times$ Baseline result, and subject experiences liver- related symptoms (e.g., anorexia, nausea, vomiting, right upper quadrant pain, pruritus, cholestasis)	Interrupt study drug for at least 15 days. Initiate potential DILI evaluation for alternative etiologies, and repeat liver profile and PT/INR within 2 to 3 business days from the date results are received for review, and place subject under “close observation” as defined in the DILI guidance.

Abbreviations: ALP = alkaline phosphatase; ALT = alanine aminotransferase; AST = aspartate aminotransferase; DILI = drug-induced liver injury; GGT = gamma-glutamyltransferase; INR = international normalized ratio; PT = prothrombin time; ULN = upper limit of normal.

*Close observation as defined in the FDA DILI guidance (i.e., laboratory testing and physical examination 2 to 3 times per week. Study drug is to be restarted only if a firm alternative etiology is “identified” and the liver tests return to ‘baseline’ levels).

Note the following:

The ‘baseline’ result for any laboratory parameter is the average of the Screening visit result, the Day 1 visit result and any unscheduled visit that occurred during the Screening period.’

Study drug interruption refers to cessation of study drug intake, but with the possibility that intake may re-start at a later date if certain requirements described in this appendix are confirmed.

Conversely, study drug discontinuation refers to cessation of study drug intake and without the possibility that intake may restart at a later date. However, such a subject should remain in the study, continue to undergo ‘close observation’ where required, and other scheduled study assessments.

If a subject sustains a liver test elevation but remains eligible to continue study drug intake in parallel with ‘close observation’, and ‘close observation’ is not possible then study drug intake should be interrupted until it is possible for the subject to undergo further assessment.

Close observation as defined in the FDA DILI guidance i.e., laboratory testing and physical examination 2 to 3 times per week. Study drug is to be restarted only if a firm alternative etiology is “identified” and the liver tests return to ‘baseline’ levels.

2. Elevation of aminotransferase and total bilirubin or cholestatic liver test markers:

Analyte	Event during the study	Action
TB + AST or ALT	↑ TB >2 mg/dL and ↑ ALT or ALT \geq 3 × Baseline or 5 × ULN (whichever comes first)	Interrupt study drug for at least 15 days. Initiate potential DILI evaluation for alternative etiologies. Repeat liver profile and PT/INR within 2 to 3 business days from the date results are received for review, and place subject under “close observation” as defined in the DILI guidance.
TB, ALP, or GGT	↑ TB >2 mg/dL and ALP or GGT ↑ >2 × ULN	Study drug can be re-started only if a firm competing etiology is identified and the liver tests return to Baseline levels.
TB OR INR + symptoms (regardless of any magnitude AST/ALT elevation)	Elevation ↑ TB >2 mg/dL OR INR \geq 1.5 and Indicators of immunological reaction (i.e., rash or >5% eosinophilia), or appearance of liver-related symptoms, e.g., anorexia, nausea, vomiting, right upper quadrant pain, pruritus, cholestasis.	Permanently discontinue study drug. Initiate potential DILI evaluation for alternative etiologies. Repeat liver profile and PT/INR within 2 to 3 business days from the date results were received for review, and place subject under “close observation” as defined in the DILI guidance.

Abbreviations: ALP = alkaline phosphatase; ALT = alanine aminotransferase; AST = aspartate aminotransferase; DILI = drug-induced liver injury; GGT = gamma-glutamyltransferase; INR = international normalized ratio; PT = prothrombin time; TB = total bilirubin; ULN = upper limit of normal.

Note the following:

If a subject lives in a remote area, they can be tested using a local (‘non-central’) laboratory, with the results communicated to the Investigator promptly.

For subjects with Gilbert’s syndrome, a doubling of direct bilirubin concentration instead of total bilirubin concentration should be used for close monitoring and TVB-2640 discontinuation.

If either of the following criteria are met, study drug must be discontinued and the subject must be followed until the clinical and laboratory abnormalities stabilize or normalize:

- In the presence of total bilirubin elevation ($>2 \times$ ULN or $>1.5 \times$ Baseline level); with any degree of aminotransferase elevation; AND if there is appearance of symptoms i.e., fatigue, nausea, vomiting, right upper quadrant pain or tenderness, fever, rash, and/or eosinophilia ($>5\%$).
- If any total bilirubin, ALT, or AST elevation above the subject's Baseline result recurs following rechallenge with study drug.

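### Appendix A mandates no action for a first qualifying ALT/AST rise without symptoms when total bilirubin is above normal but not above 2 mg/dL

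*Protocol*

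**What the plan says.** Section 8.3 of the protocol refers the management of suspected drug-induced liver injury (DILI) to Appendix A. The appendix opens with "During the study, aminotransferase elevations are to be managed as follows" and gives two tables, called here the first and second table. They are not the numbered Tables 1 and 2 in the body of the protocol.

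**First table.** It is headed "Isolated aminotransferase elevation (i.e., total bilirubin - normal".
- ALT and AST normal at Baseline, rise to at least 5 × ULN: repeat tests and close observation.
- ALT or AST raised at Baseline, rise to at least 3 × Baseline, with or without symptoms: interruption for at least 15 days, DILI work-up, repeat tests and close observation.

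**Second table.**
- Row 1 reads "TB >2 mg/dL and ↑ ALT or ALT", with an aminotransferase trigger of 3 × "Baseline or 5 × ULN (whichever comes first". It requires interruption.
- Row 2 needs total bilirubin (TB) above 2 mg/dL with ALP or GGT above 2 × ULN.
- Row 3, labelled "TB OR INR + symptoms (regardless of any magnitude AST/ALT elevation", needs TB above 2 mg/dL or INR of at least 1.5. It also needs rash, eosinophilia or "appearance of liver-related symptoms, e.g., anorexia, nausea, vomiting, right upper quadrant pain, pruritus, cholestasis". It requires permanent discontinuation.

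**Closing criteria for mandatory discontinuation.**
- The first needs TB above 2 × ULN or above 1.5 × Baseline, with any aminotransferase elevation, "AND if there is appearance of symptoms i.e., fatigue, nausea, vomiting, right upper quadrant pain or tenderness, fever, rash, and/or eosinophilia".
- The second applies when an elevation above the subject's "Baseline result recurs following rechallenge with study drug".

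**The concern.** The two tables do not meet. The first ends at the bilirubin ULN and the second begins above 2 mg/dL. Take one aminotransferase rise and vary only the bilirubin. With a raised Baseline ALT or AST, the required action runs from interruption, to nothing mandated, to interruption. With a normal Baseline it runs from close observation, to nothing mandated, to interruption. So a subject with a mildly raised bilirubin is owed less than one with a normal bilirubin.

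This concerns subject safety. Suspected DILI is one of four event types singled out in Section 8.3, dosing lasts 52 weeks, and exclusion criterion 12 admits subjects with ALT and AST up to 5 × ULN, so the raised-Baseline rule is relevant here. Followed literally, the appendix leaves this band to the investigator's judgment.

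**Working it through.** There is no plan figure to reproduce, so the check is one of logic. Take a first rise that meets the first table's trigger, in a subject without Gilbert's syndrome, and ask which rules fire as TB varies.

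**Inputs.** The rules are those above. The bilirubin ULN is not in the documents; 1.0, 1.2 and 1.3 mg/dL are assumed (1.3 is the entry limit in exclusion criterion 14).

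**Case 1: no symptoms, rash or eosinophilia**

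| TB | First table | Second table, row 1 | Row 2 | Row 3 | Closing 1 | Closing 2 |
|---|---|---|---|---|---|---|
| ≤ ULN | fires | no | no | no | no | no |
| > ULN to 2.0 | no | no | no | no | no | no |
| > 2.0 | no | fires | only if ALP or GGT > 2 × ULN | no | no | no |

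Row 3 and the first closing criterion fail for want of symptoms, and the second fails because this is a first rise. Width of the empty band = 2.0 − ULN:
- ULN 1.0: 2.0 − 1.0 = 1.0 mg/dL
- ULN 1.2: 2.0 − 1.2 = 0.8 mg/dL
- ULN 1.3: 2.0 − 1.3 = 0.7 mg/dL

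This holds at any Baseline TB. The band stays empty with ALT at 10 × Baseline and 20 × ULN. With INR 1.6 and ALP or GGT at 3 × ULN as well (checked at TB 1.8, ULN 1.2), still no rule fires without symptoms.

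**Case 2: a symptom on the first closing criterion's list (for example nausea), INR below 1.5**

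The first closing criterion fires once TB exceeds 1.5 × Baseline. Its other limb, 2 × ULN, is 2.0, 2.4 or 2.6 mg/dL, so it is never passed inside the band. The gap runs from the ULN to 1.5 × Baseline TB, and no further than 2.0. It exists only if Baseline TB exceeds ULN/1.5.

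| ULN | Baseline TB needed (ULN/1.5) | Width at Baseline TB 1.0 (1.5 − ULN) |
|---|---|---|
| 1.0 | > 0.67 | 0.5 |
| 1.2 | > 0.80 | 0.3 |
| 1.3 | > 0.87 | 0.2 |

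At Baseline TB 1.3 the upper end is 1.5 × 1.3 = 1.95 mg/dL.

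**Case 3: only a symptom that row 3 names and the closing list omits (anorexia, pruritus, cholestasis), INR below 1.5**

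Row 3 does not fire (TB not above 2, INR below 1.5), nor does the first closing criterion. The gap is again the ULN to 2.0 mg/dL at any Baseline TB. Example with ULN 1.2, Baseline TB 0.6, current TB 1.6: 1.6/0.6 = 2.67 × Baseline and 1.6/1.2 = 1.33 × ULN. With nausea, drug must be discontinued; with pruritus alone, no rule applies.

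**Two possible repairs.** (A) Let the first table run to TB ≤ 2 mg/dL. (B) Start row 1 of the second table at TB above the ULN. Row 1 has a wider aminotransferase trigger, so B reaches further. Illustration with an assumed ALT ULN of 40, bilirubin ULN 1.2, TB 1.5, no symptoms:

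| ALT change | × ULN | × Baseline | Under A | Under B |
|---|---|---|---|---|
| 80 to 240 | 6.0 | 3.0 | interrupt | interrupt |
| 30 to 200 | 5.0 | 6.7 | close observation | interrupt |
| 25 to 75 | 1.9 | 3.0 | none | interrupt |
| 80 to 210 | 5.25 | 2.6 | none | interrupt |
| 12 to 36 (still normal) | 0.9 | 3.0 | none | interrupt |

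The last three rises never meet the first table's trigger. A Baseline above 5/3 = 1.67 × ULN reaches 5 × ULN before 3 × Baseline. Under A, every rise that does meet the trigger is covered in all three cases.

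**The case against.** - **Section 8.3 is mandatory.** Its lead-in requires permanent discontinuation for the listed events, and suspected DILI is listed. But it also says subjects are handled as each bullet indicates, and the DILI bullet defers to Appendix A, which itself allows observation or interruption. It supplies no rule for the band.
- **Appendix A presupposes close observation.** One sentence says to interrupt drug if close observation is not possible for a subject continuing with a liver test elevation, with no bilirubin limit. It does not order observation at any bilirubin level.
- **The intended split may be 2 mg/dL.** The two headings look complementary, and 2 mg/dL is the threshold in every row of the second table that names a bilirubin value. That is probably what was meant. But normal cannot naturally mean up to 2 mg/dL in a protocol that excludes entry above 1.3, so the text needs correcting.
- **No action already begun is withdrawn.** This stands. The restart rule keeps an interrupted subject off drug, so the gap concerns a first presentation with TB already in the band.
- **The symptom cases are finely parsed.** They depend on reading the closing list as complete because it is introduced by i.e. Case 1 does not depend on this.
- **Other provisions exist.** Sections 7.3, 8.3, 12.1.5 and 12.2.5 allow interruption, withdrawal and repeat tests, and require follow-up of related adverse events. None sets the missing action. Section 8.3 also cites a Study Manual that was not available, so the point concerns the protocol text only.
- **It is late.** This also stands. The SAP cites protocol version 4.0 of 06 September 2023, and the synopsis estimates last subject completed in September 2023.

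**Conclusion.** The concern holds. For a first ALT/AST rise meeting the first table's trigger, without symptoms, rash or eosinophilia, Appendix A mandates nothing while total bilirubin is above the ULN and not above 2 mg/dL. The band is 0.7 to 1.0 mg/dL wide for an assumed ULN of 1.0 to 1.3 mg/dL, and it exists for any ULN below 2 mg/dL. A gap of equal or smaller width remains for some subjects with symptoms and INR below 1.5.

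The conclusion rests on reading the first table's heading as TB no higher than the ULN. It excludes subjects with Gilbert's syndrome, for whom direct bilirubin is used. Frequency cannot be estimated from the documents. Confidence in the reading is high; the practical effect in this study depends on how many subjects remain on drug, which is not stated.

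**What to change.** Change the bilirubin condition in the first table's heading from normal to ≤ 2 mg/dL, and correct the repeated ALT in row 1 of the second table to ALT or AST, as that row's own label has it. Every rise meeting the first table's trigger then meets a row. Where the first closing criterion is also met, its mandatory discontinuation still applies.

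Repair B is the broader alternative. It would interrupt normal-Baseline subjects instead of only observing them, and would capture rises outside the first table's trigger, including some still within the normal range. Under repair A, rises outside that trigger still have no mandated action up to 2 mg/dL unless another rule applies. The sponsor's medical lead should choose, and should also say whether the first table applies to subjects with Gilbert's syndrome whose total bilirubin is above normal.

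The cost is one heading edit and one typographical correction, by amendment or safety letter. Some additional subjects, number unknown, would be interrupted for at least 15 days or placed under close observation with testing and examination 2 to 3 times a week.
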